5. GENERAL METHODOLOGY AND CONVENTIONS

5.1. Hypotheses and Decision Rules

Not applicable as this is a descriptive study.

5.2. General Methods

5.2.1. Methods to Manage Missing Data

In general, only subjects with available data will be included in the statistical analysis.

Missing values for antibody titer at 38 and 46 months will neither be replaced nor estimated. Any missing values at later time points (ie, 58, 70, 82, 94, 106 and 118 months) due to early withdrawal or second booster vaccination within this current study, will be estimated if at least three data points are available, assuming an exponential decline in antibody titers in time (calculated as described in [Section 5.2.2.1](#)).

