## 7. STUDY PURPOSE AND OBJECTIVES

### 7.1 Study Purpose

The main purpose of this study is to assess the seropersistence of TBE virus antibodies in children, adolescents and young adults who received the first booster vaccination with either FSME-IMMUN 0.25 ml Junior or FSME-IMMUN 0.5 ml in Study 700401.

The current protocol is being conducted to obtain prospective clinical trial data on long-term TBE serum antibody persistence beyond the first booster and to verify the current TBE booster recommendations. The study investigates TBE virus antibody persistence at yearly intervals from approximately 3 years (38 months) to 10 years (118 months) after the first booster vaccination (as applicable). The decision whether to administer the second booster vaccination in this study and the timing thereof will depend on the level of serum TBE antibodies detected at the defined assessment time points. Subjects who may not be protected against TBE for an entire further tick season (NT titer  $\leq$  20 and / or ELISA value  $\leq$  126 VIE U/ml), should be invited to receive the booster vaccination at either the 40, 48, 60, 72, 84, 96, 108, or 120 month time point. Recommendations as to whether or not to administer the booster vaccination will be given by the Sponsor on an individual basis. The Data Monitoring Committee (DMC) will be consulted for their opinion in case of inconclusive serological data (e.g. contradictory results in ELISA and NT).

The cut-off level for an NT titer of 1:20 as described above was chosen based on the annual decline rate determined in the precursor studies 209 and 700401i, in which antibody persistence was investigated 1, 24, 34, 46 and 58 months after completion of the TBE primary vaccination series. Annual decline rates were calculated on the basis of log-transformed antibody titers. The mean annual decline rates determined for subjects aged 1-2 years, 3 – 6 years and 7 – 15 years were -0.50, -0.38 and -0.46, respectively. Therefore, an NT titer of 20 at a specified time point would on average be reduced to 12.2, 13.6 or 12.6 within a year for the 3 age categories, respectively, which is just above the cut-off level for seropositivity (NT  $\geq$  1:10). Also, subjects should receive the booster vaccination in the current study if their ELISA value has declined below the level of seropositivity, i.e.  $\leq$  126 VIE U/ml.

---

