5.2.2. Analyses for Continuous Data

5.2.2.1. Annual Decline Rate of Antibody Response

To calculate the annual decline rate of antibody response on NT, the NT titers measured at each blood sampling time point (including Study 700401 post-booster Visit, and Study B9371021 visits 1, 2, 3, 6, 7, 8, 9, 10) will be logarithmically transformed. These log transformed data will be used as dependent variable, with days after first booster dose (from study 700401) as independent variable, to calculate the annual decline rate, using regression model for each subject. The slope from the model multiplied by 365 is considered as the estimated annual decline rate for each subject. Summary statistics on the estimated annual decline across all subjects will then be presented.

Subjects with missing assay data at 38-month and 46-month after the first booster dose will not be included in this analysis. In addition, subjects with a more than 4-fold increase in TBE antibodies between successive visits will be excluded from the analysis.

Calculation of the decline rate:

- Perform linear regression of the log transformed results for each subjects;
- Annual decline rate=slope of regression line * 365;
- Calculate descriptive statistics for the annual decline rate across all subjects.

A similar analysis will be performed for the ELISA data.

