5.2.3. Analyses for Binary Data

All of the binary endpoints will be descriptively summarized along with the exact 2-sided 95% confidence interval (or Clopper-Pearson confidence limit) for the proportion. The exact confidence interval for proportion will be computed using the F distribution. If r equals the number of responses and n equals the number of subjects, then it follows that $p = r / n$ is the estimate of the proportion of responses. An exact 95% confidence interval can be computed by solving the following 2 equations. For the lower limit p_L , use:

$$p_L = \frac{rF_L}{(rF_L + (n - r + 1))} \text{ and for the upper limit } p_U, \text{ use } p_U = \frac{(r + 1)F_U}{(n - r) + (r + 1)F_U}$$

where F_L is the quantile from the F distribution for $\alpha=0.025$, with numerator degrees of freedom equal to $2r$ and denominator degrees of freedom equal to $2(n-r+1)$. F_U is the quantile from the F distribution for $\alpha=0.975$, with numerator degrees of freedom equal to $2(r+1)$ and denominator degrees of freedom equal to $2(n-r)$. When r equals 0, F_L should be set equal to 1.0 so p_L equals 0. When r equals n , F_U should be set equal to 1.0 so p_U equals 1. The confidence interval using the F distribution is described in Collett (1991¹) and implemented in SAS procedure (ie, PROC FREQ).

To estimate the seropositivity rate as determined by NT from approximate 3 years to 10 years after the first booster vaccination (from precedent study 700401), the proportion of subjects with $NT \geq 10$ at each blood sampling time point (including extrapolated from regression model for subjects with booster dose or early withdrawals from [Section 5.2.2.1](#), and the available assay results) after the first booster will be summarized with the exact 95% CI. Similarly, the proportion of subjects with $ELISA > 126$ at each blood sampling time point (including extrapolated results) after the first booster will be summarized with the exact 95% CI. The analysis will be applied to '[Per Protocol](#)' Analysis Set. For [mITT Population](#), which will include all available NT titers and ELISA concentrations, ie, no extrapolation from regression model will be done for subjects with booster dose or early withdrawals.

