6. ANALYSES AND SUMMARIES

6.1. Analysis of Primary Immunogenicity Endpoints

The primary analysis for the primary objective will be based on the evaluable immunogenicity population for the primary endpoints. 95% exact confidence intervals (CIs) will be presented along with the seropositive rate on NT as described in [Section 5.2.3](#). Missing values handling were described in [Section 5.2.1](#).

Additional analysis on the primary endpoints will also be applied to the mITT population.

P-values from the logistic regression will be presented to assess the relation of seropositive rate with the covariates (per-protocol population only).

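### Subjects boosted after Visit 1 have no observed or estimated value from Month 46 on, so the Month 46 NT seropositivity rate can be biased upward and the mITT analysis would not show it

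*SAP*

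**What the plan says.** The primary endpoint is the NT seropositivity rate (NT ≥10) at each yearly draw after the first booster, and after the second booster (SAP 3.1.1).

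- **Missing values.** SAP 5.2.1: "Missing values for antibody titer at 38 and 46 months will neither be replaced nor estimated". Values missing from Month 58 on "due to early withdrawal or second booster vaccination within this current study, will be estimated if at least three data points are available". Protocol 13.3 sets the same Month 38/46 rule and the same three-point minimum.
- **Points that count.** SAP 5.2.2.1 fits each subject's regression to the draws after the first booster ("including Study 700401 post-booster Visit, and Study B9371021 visits 1, 2, 3, 6, 7, 8, 9, 10"). Visit 5, the draw after the second booster, is not listed.
- **Who is drawn.** Protocol 10.3.2.1 and Table 20.2-1, footnote b, limit Visits 2, 3 and 6 to 10 to subjects not yet given the second booster.
- **Who is boosted.** Subjects with NT ≤20 and/or ELISA ≤126 VIE U/ml are invited (SAP 2.2.2; Protocol 8.1). The ELISA limit is the seropositivity limit itself: "subjects should receive the booster vaccination in the current study if their ELISA value has declined below the level of seropositivity" (Protocol 7.1).
- **Analysis sets.** The per-protocol rates include extrapolated values. For mITT, "no extrapolation from regression model will be done for subjects with booster dose or early withdrawals" (SAP 5.2.3). SAP 6.1 adds: "Additional analysis on the primary endpoints will also be applied to the mITT population".

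**The concern.** SAP 5.2.1 names the second booster as a reason for estimating a missing value, yet its conditions leave out the subjects boosted earliest. Those subjects leave because their antibody was low. The NT trigger takes in every subject with NT <10, and the ELISA trigger takes in every ELISA-seronegative subject. With full uptake, the Month 46 rate would describe only subjects who had NT >20 and ELISA >126 at Visit 1.

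The study is descriptive, so the yearly rates and their intervals are its result. Protocol 6.6.2 says the results will help to identify the best booster interval. A rate calculated without subjects removed for low antibody can overstate persistence, and the per-protocol and mITT figures would then agree with each other while sharing the same gap.

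**Working it through.** **1. The plan's own figures**

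- *Precision.* Protocol 13.1 gives at most 5.8 points with 175 subjects and a rate near 90%. The exact (Clopper-Pearson) lower limit lies 5.38 points below 158/175 (90.3%) and 5.76 points below 154/175 (88.0%). The figure reproduces as an upper bound over that region.
- *Decline.* Protocol 7.1 gives annual log-scale declines that "were -0.50, -0.38 and -0.46, respectively", and projects NT 20 to 12.2, 13.6 and 12.6 after a year. 20·exp(−0.50) = 12.13, 20·exp(−0.38) = 13.68 and 20·exp(−0.46) = 12.63. These agree within rounding of the rates, so the logarithm is natural.

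**2. Usable points for a subject boosted after Visit 1**

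- Study 700401 post-booster draw (1) + Visit 1 (1) = 2.
- Month 46: not drawn, and never estimated.
- Months 58 to 118: not drawn, and 2 < 3, so not estimated.
- mITT: observed values only, so this subject is absent there too.

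A subject boosted after Visit 2 has three points and can be extrapolated from Month 58. SAP 5.2.2.1 also states: "Subjects with missing assay data at 38-month and 46-month after the first booster dose will not be included in this analysis". That may mean either value missing or both; the count above gives the same result under both readings.

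**3. Who would be NT-negative at Month 46**

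The Visit 1 titre that declines on average to 10 is 10·exp(rate × months/12).

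| Visit 1 | Months to Month 46 | Rate 0.38 | Rate 0.46 | Rate 0.50 |
|---|---|---|---|---|
| Month 38 | 8 | 12.9 | 13.6 | 14.0 |
| Month 34 (29 subjects, Protocol 6.3) | 12 | 14.6 | 15.8 | 16.5 |

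NT 20 at Month 38 projects to 14.3 to 15.5 at Month 46, which is still positive. The rates were measured after the primary series; applying them after the first booster is an assumption.

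**4. Size at Month 46**

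Of the 179 enrolled (SAP 2.2.2), let k be dropped subjects who would be NT <10 at Month 46, m dropped subjects who would be positive, and n negatives still observed.

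- Full-cohort rate: (179 − k − n)/179
- Reported rate: (179 − k − m − n)/(179 − k − m)
- Bias: k/179 + n/179 − n/(179 − k − m), which never exceeds k/179

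The bias is upward when the share of negatives among the dropped, k/(k + m), exceeds the share among those retained, n/(179 − k − m).

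| k | m | n | Full cohort | Reported | Exact 95% CI of reported | Bias (points) |
|---|---|---|---|---|---|---|
| 0 | 10 | 2 | 98.9% | 98.8% | 95.8–99.9 | −0.1 |
| 2 | 0 | 0 | 98.9% | 100% | 97.9–100 | +1.1 |
| 4 | 0 | 0 | 97.8% | 100% | 97.9–100 | +2.2 |
| 6 | 0 | 2 | 95.5% | 98.8% | 95.9–99.9 | +3.3 |
| 10 | 0 | 0 | 94.4% | 100% | 97.8–100 | +5.6 |
| 11 | 0 | 0 | 93.9% | 100% | 97.8–100 | +6.1 |

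With no negatives left among those observed, k = 4 is the first value at which the reported interval misses the full-cohort rate. With two left, it is k = 6. The planned 5.8 points is exceeded only from k = 11.

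**The case against.** The strongest reply is that this is a stated restriction set in Protocol 13.3 and carried into the SAP, and that the effect may be negligible. Month 38 is unaffected, because everyone is drawn before boosting. Post-booster results are presented by year (SAP 5.2.3), and SAP 6.4.1 tabulates draws per visit and subjects vaccinated, so a reader could probably work out how many left after Visit 1. Study 700501 found every subject seropositive about three years after a first booster (Protocol 6.4.2), although by ELISA and/or NT and after a different primary vaccine. SAP 6.2 allows for there being no ELISA-seronegatives.

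Most of this stands. It limits the size and rules out replacing the pre-specified analysis. It does not supply the missing values, and no planned table states how many subjects are extrapolated or dropped at each visit.

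Three stronger readings are tempting, and the documents do not support them:

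- *Every boosted subject is a hidden negative.* Subjects boosted on ELISA alone, or with NT of about 14 to 20 at Month 38, would on average still be NT-positive at Month 46.
- *The rates from Month 58 on are inflated too.* Subjects boosted later can be extrapolated from three or more points, which may shift the rate by an amount not assessed here. No net direction follows.
- *The SAP offers mITT as a sensitivity check on persistence.* It calls mITT a secondary population and an additional analysis. The point is only that agreement between the two sets would not be evidence against this bias.

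**Conclusion.** The gap follows from the text: subjects boosted after Visit 1 contribute nothing to the first-booster rates from Month 46 on, in either analysis set, and they are selected for low antibody. Confidence in this mechanism is high.

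The bias is conditional. The Month 46 NT rate is generally too high if some of these subjects had NT <10 at Visit 1, or were below about NT 12.9 to 14.0 at a Month 38 draw (14.6 to 16.5 at a Month 34 draw). Those limits rest on the Protocol 7.1 mean decline rates and on nominal visit times.

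The size is unknown, because the documents give neither the number boosted after Visit 1 nor their titres. It cannot exceed k/179. It is zero if nobody was boosted after Visit 1 and about zero if only NT-positive subjects were lost. A reader might infer that the Month 46 rate is in fact inflated; the documents show only that it can be. The point is worth fixing because it touches the primary endpoint and the remedy is cheap.

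**What to change.** Change the analysis only; leave the booster rule alone. Keep the analysis of Protocol 13.3 and SAP 5.2.1 as pre-specified. Add to SAP 5.2.3 a separately labelled supplementary per-protocol analysis, marked as added after the 5-year interim analysis (SAP 7), for example:

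> At Month 46 and each later first-booster visit, subjects given the second booster who have neither an observed nor an extrapolated value stay in the denominator. Those seronegative in that assay at their last pre-booster draw count as seronegative. The others are counted once all as seronegative and once all as seropositive, giving bounds. Boosted subjects with at least three points are handled as in Section 5.2.1.

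Report for each visit the numbers observed, extrapolated and dropped because of the second booster. If few were dropped, the bounds will be narrow and will settle the matter.

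The cost is slight extra programming and a possibly less favourable Month 46 rate. No new samples or visits are needed. Because the analysis assigns a Month 46 status that Protocol 13.3 declines to estimate, it must stay supplementary.

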### 10.3.2 Study visits

#### 10.3.2.1 Blood draw (investigation of TBE antibody persistence)

**Visit 1:** 38 months  $\pm$  60 days after the booster vaccination in Study 700401ii.

All subjects who were administered the first booster vaccination in Study 700401 will be invited for this visit. Subjects with relatively low TBE serum antibody levels (as described further) will proceed to Visit 4 (Booster vaccination) and Visit 5 (Post-booster Visit), as applicable (see [Figure 20.1-1](#), [Supplement 20.1](#)).

**Visit 2:** 46 months  $\pm$  30 days after the booster vaccination in Study 700401.

This visit will only be applicable for those subjects who have not yet received the second booster vaccination. Subjects with relatively low TBE serum antibody levels will proceed to Visit 4 and Visit 5 (see [Figure 20.1-1](#), [Supplement 20.1](#)).

**Visit 3:** 58 months  $\pm$  30 days after the booster vaccination in Study 700401.

This visit will only be applicable for those subjects who have not yet received the second booster vaccination. Subjects with relatively low TBE serum antibody levels will proceed to Visit 4 and Visit 5 (see [Figure 20.1-1](#), [Supplement 20.1](#)).

**Visit 6:** 70 months  $\pm$  30 days after the booster vaccination in Study 700401.

**Visit 7:** 82 months  $\pm$  30 days after the booster vaccination in Study 700401.

**Visit 8:** 94 months  $\pm$  30 days after the booster vaccination in Study 700401.

**Visit 9:** 106 months  $\pm$  30 days after the booster vaccination in Study 700401.

**Visit 10:** 118 months  $\pm$  30 days after the booster vaccination in Study 700401.

These additional blood draw visits are only applicable for subjects who have not yet received the second booster vaccination. Subjects with relatively low TBE serum antibody levels will proceed to Visit 4 and Visit 5 (see [Figure 20.1-2](#), [Supplement 20.1](#)).

---

ii The 29 subjects who were administered the first booster vaccination at the 4 year time point in Study 700401 and who will enter the current study in 2010 will have their Visit 1 at 34 months  $\pm$  60 days. For Visit 2 and Visit 3 the schedule is to be followed as described in the protocol.

The following assessments will be performed:

- Verification of the signed and dated informed consent/assent of the subject prior to any procedures being done (at Visit 1 ONLY);
- Inclusion and exclusion criteria (see Section 9.1 and Section 9.2);

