### 13.3 Handling of Missing, Unused, and Spurious Data

Only subjects with available data will be included in the statistical analysis. Missing values for antibody titer at 38 and 46 months will neither be replaced nor estimated. Any missing values at later time points (i.e. 58, 70, 82, 94, 106 and 118 months) will be estimated if at least three data points are available, assuming an exponential decline in antibody titers in time.

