2.2.2. Study Subjects Selection and Process

A total of 179 children, adolescents and young adults who received their first TBE booster vaccination in the precedent Study 700401 were enrolled to assess seropersistence of TBE antibodies at yearly intervals from approximately 3 years (38 months) to 10 years (118 months) after the first booster vaccination (as applicable), as well as antibody response to a second booster vaccination with either FSME-IMMUN 0.25 ml Junior or FSME-IMMUN 0.5 ml according to the subject's age.

Subjects who may not be protected against TBE for an entire further tick season (NT titer ≤ 20 and / or ELISA value ≤ 126 VIE U/ml) will be invited to receive the second booster vaccination at either the 40, 48, 60, 72, 84, 96, 108, or 120 month time point.

Figure 1. Study Design

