4. ANALYSIS SETS

4.1. Full Analysis Set

An All-Enrolled Population will be defined as the Full Analysis Set, which consists of all subjects enrolled into the study. Any subjects who consented are included in the population. Subject disposition, history of tick bites, and demography will be presented for this population.

4.2. 'Per Protocol' Analysis Set

This analysis set is the primary analysis population for immunogenicity.

This Per-Protocol population includes subjects who:

1. Have been enrolled (consented) and meet all inclusion/exclusion criteria at all visits.
2. Have available assay results (ELISA or NT) at any blood sampling visit.
3. Have no other major protocol violations.

Above listed items 1 & 2 will be determined by computerized checks of the data, while item 3 will be determined by clinical review as these are considered as major protocol violations per the original protocol, which will eventually be entered into the database from Protocol Deviation (PD) case report form entries.

Subjects with major protocol deviations will be excluded from the primary analysis population, or in some instances, the ELISA and NT results affected by a protocol deviation at certain visit(s) will be excluded from the analysis.

If a subject meets the exclusion criterion 2, which is that subject has a history of infection with or vaccination against other flaviviruses (eg, Dengue fever, yellow fever, Japanese B encephalitis) since his/her first booster vaccination in Study 700401, the subject's affected ELISA results will be excluded from the analysis due to cross-reactivity. There is no cross-reactivity with the NT, so the NT results will be included in the analysis. The subject will be included in Per-Protocol population, under condition that he/she satisfies the rest of the conditions in above items 1 to 3.

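### SAP 5.2.1 narrows the protocol's rule for estimating late missing titres without giving a reason, so an unboosted subject who misses one visit leaves the per-protocol rate at that visit

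*SAP*

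**What the plan says.** **Protocol 13.3** sets the rule without reference to the reason for missingness: "Any missing values at later time points (i.e. 58, 70, 82, 94, 106 and 118 months) will be estimated if at least three data points" exist for the subject, under an assumed exponential decline. Missing values at Months 38 and 46 are never estimated.

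**SAP 5.2.1** keeps the months, the three-point minimum and the decline model, but limits the rule to values missing "due to early withdrawal or second booster vaccination within this current study, will be estimated if at least three data points are available". Everything else falls under its default: "In general, only subjects with available data will be included in the statistical analysis".

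The limit is repeated where results are produced. SAP 5.2.3, which covers the seropositivity rates, describes the data as "including extrapolated from regression model for subjects with booster dose or early withdrawals from" the per-subject regression, plus the available results. SAP 5.2.2.2 (GMT/GMC) and 5.2.2.4 (reverse cumulative distribution curves) follow the same pattern. SAP 5.2.3 also carries the extrapolated values into the logistic regression.

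The set affected is the per-protocol set, of which SAP 4.2 says: "This analysis set is the primary analysis population for immunogenicity". The mITT analysis uses no extrapolation.

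Two design features matter. A second booster is offered at "NT titer ≤ 20 and / or ELISA value ≤ 126 VIE U/ml" (SAP 2.2.2). For Visits 6 to 10, Protocol 10.3.2.1 says: "These additional blood draw visits are only applicable for subjects who have not yet received the second booster vaccination". It sets the same condition for Visits 2 and 3.

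**The concern.** SAP section 2 says that the SAP gives further detail on the protocol's methods. Here it narrows one of them, for the primary endpoint, and gives no reason. The revision history does not mention the change, although that log covers only the step from version 1.0 to 1.1.

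The narrower rule treats similar subjects unevenly. A subject seen at Months 38, 46 and 58 who then withdraws has three points and receives modelled values as far as Month 118, 60 months past the last draw. A subject seen at Months 38, 46, 58, 70 and 94 who missed only Month 82 receives no Month 82 value, although the same regression is available with draws on both sides of the gap.

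The omissions also fall on one side. Once a booster is given, the subject cannot miss a later persistence draw in the sense that matters here: with three points, the value is always filled in. Only subjects still under follow-up can have a gap that stays empty, and those are mostly subjects whose antibody has stayed above the booster threshold. Even if gaps are completely random among them, the pooled rate gives the boosted group more weight than the protocol rule would.

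**Working it through.** **1. The plan's own figures.** Protocol 13.1 states that with 175 subjects and a rate near 90%, the 95% interval extends no more than 5.8% from the observed rate. Clopper-Pearson limits (the SAP 5.2.3 method) at n = 175 give these distances to the lower limit: 158/175, 5.38 points; 157/175, 5.48; 154/175 (88.0%), 5.76. The figure reproduces as an upper bound for rates from about 88%.

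Protocol 7.1 gives mean annual declines of -0.50, -0.38 and -0.46 on the log scale, and says that a titre of 20 falls to 12.2, 13.6 or 12.6 in a year. With natural logs, 20 × exp(decline) = 12.13, 13.68 and 12.63, which agrees within the rounding of the rates.

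**2. Who is estimated at Months 58 to 118.**

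| Subject | Protocol 13.3 | SAP 5.2.1 |
|---|---|---|
| Unboosted, at least 3 points, misses one draw and returns | Estimated | Omitted at that visit |
| Boosted, at least 3 points | Estimated | Estimated |
| Withdrew early, at least 3 points | Estimated | Estimated |
| Boosted after Visit 1 (at most 2 points: Study 700401 post-booster and Month 38) | Not estimated | Not estimated |

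The documents differ only in the first row.

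**3. Which way the first row pushes.** A subject still unboosted was generally above NT 20 at the previous draw. One year at the protocol's mean decline leaves about 12.1 to 13.7 or more, against a seropositivity cut-off of 10. The omitted values are therefore mostly likely positives.

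**4. Size relative to the protocol rule.** Assume that N subjects have a value under the protocol rule, that the rate is p, and that m of the positives are omitted under the SAP rule. The change is (Np - m)/(N - m) - p = -m(1 - p)/(N - m). N = 175 is the planning figure; m is assumed.

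| m (share of 175) | p = 90% | p = 80% |
|---|---|---|
| 1 (0.6%) | -0.06 points | -0.11 |
| 5 (2.9%) | -0.29 | -0.59 |
| 9 (5.1%) | -0.54 | -1.08 |
| 17 (9.7%) | -1.08 | -2.15 |

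For example, at 90% with m = 9: (157.5 - 9)/(175 - 9) = 148.5/166 = 89.46%, a change of -0.54.

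**5. Net direction.** Let k seronegative subjects boosted after Visit 1 also be absent, as they are under both rules. At 90% and m = 9, k = 1 gives 148.5/165 = 90.0%, a change of 0.00. With k = 5, 148.5/161 = 92.24%, a change of +2.24. One such subject cancels nine omitted positives.

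**6. Simulation check (all inputs assumed).** N = 175; log titres around a start of 500 (SD 0.9 natural-log units); mean annual slope -0.3 (SD 0.1); measurement SD 0.3; booster at NT 20 or below; 2% withdrawal per visit; 2%, 5% or 10% random missed visits. Runs were made with and without an extra early drop of 1 log unit before Month 38, and with the Study 700401 value counted or not counted among the three points; 60 replicates each. The SAP rule minus the protocol rule lay between 0 and -2.2 points at Months 58 to 118 and was never positive. The SAP rule minus the simulated true rate ran from about +8 points (Month 58) to about -10 (Months 106 and 118). The widest departures came with the early drop, where decline is not log-linear.

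**The case against.** The strongest defence is that the restriction has a purpose. Values missing after a booster are missing because of antibody level, so an available-case rate would be too high; extrapolation addresses that. A sporadic missed visit can reasonably be left as missing, and a denominator that varies with attendance occurs in any available-case analysis, including the mITT one. This would be a fair rationale, but the SAP does not state it. It also does not remove the imbalance, because the two kinds of subject are pooled in one rate.

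Several limits stand in full:

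- **Net bias.** A reader might infer that the per-protocol rate is biased downward against the truth. The documents do not support that: subjects boosted after Visit 1, who may have the lowest titres, are lost under both rules, which pushes the rate up.
- **Who leaves.** Those kept by extrapolation are not all low-titre. Withdrawal can be voluntary or loss to follow-up (Protocol 9.5), and ELISA alone can trigger a booster while the primary endpoint is NT.
- **Who stays.** Not every unboosted subject is above the threshold, since an invited subject may decline or be ineligible for vaccination (Protocol 9.3).
- **Certainty of the filled value.** It would come from a straight line over the whole period, which under SAP 5.2.2.1 includes the Study 700401 post-booster value. It is not a local interpolation between neighbouring draws, so it is better placed than a long extrapolation but not certain.
- **Three points.** SAP 5.2.1 does not say whether the Study 700401 value counts. A subject who withdrew after Month 46 is extrapolated only if it does.

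The study is descriptive (SAP 5.1), so no decision rule depends on the shift.

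**Conclusion.** The two documents give different rules for the primary analysis, and the narrower one is unexplained. Relative to the protocol rule, the SAP rule lowers the per-protocol NT seropositivity rate by about 0.1 to 1 point at 90% with up to 10% missed visits, and by up to about 2 points at 80%. This assumes that missed visits are unrelated to titre, that the omitted subjects would have been estimated seropositive, and that the counts are those assumed above. The effect is small beside an interval distance of about 5.4 points at the planning rate. An effect on GMTs is plausible in the same direction but was not quantified.

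The conclusion is confined to the comparison of the two rules. The sign of any bias against the true rate cannot be settled from the documents. The point is worth correcting because it concerns the primary analysis and costs almost nothing to resolve.

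**What to change.** 1. In SAP 5.2.1, delete the clause that limits estimation to early withdrawal or second booster, so that the Protocol 13.3 rule also covers intermittent missed visits at Months 58 to 118. Align SAP 5.2.2.2, 5.2.2.4 and 5.2.3.
2. State that results removed under SAP 4.2, for a protocol deviation or for flavivirus cross-reactivity in ELISA, are not refilled by the model. Without this sentence, the wider rule could be read as restoring them.
3. State whether the Study 700401 post-booster value counts among the three points.
4. In the per-visit tables, report the numbers observed, interpolated, extrapolated (by reason) and omitted.

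The cost is SAP wording and a few table columns. The per-subject regressions are already planned, and no new data are needed. The small downside is a few more model-estimated values per visit, which item 4 makes visible.
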